depression taking chlorpromazine and lithium, both medications known to increase seizure risk. To date, there has been a single report of an induced focal motor seizure during single pulse TMS of an epilepsy patient with a known epileptic focus in the left frontal cortex (Classen et al 1995). These few reported seizures were not associated with long term adverse outcome (Schrader et al. 2004).

In the event of a concurrent seizure during stimulation, one or more co-investigators with specialty training in epilepsy will be present to monitor for adverse effects and monitor for exacerbation of seizure type and frequency. If there is immediate cause for concern the PI and Co-PI will make necessary medical arrangements, including direction to the emergency room if needed. If any other unanticipated adverse events occur which are thought to be related to study intervention, the patient will be withdrawn from further participation in the study. Though our clinical trial will include a safety-monitoring plan, there are no known severe or lasting adverse effects with TMS using proper set-up.

1. Though minimal, due to the concern of potential increased seizures with TMS, we will monitor increase in seizure severity attributable to TMS by identifying all instances of generalized tonic clonic seizures after TMS treatments (defined as occurring within 20 minutes of stimulation). In addition, subjects will be asked to keep a seizure diary for the 7 days prior to stimulation, and the 7 days after stimulation. Instances where seizure frequency increased after TMS will be reported to the IRB within 1 week.
2. If a self-limited, short (<5 min) complex partial seizure or evolution into generalized tonic clonic seizures occur during the procedure, TMS mapping will stop for that day.
3. In case of, pain, transient hearing impairment, the patient's primary epileptologist will be notified and appropriate medical followup will be arranged.
4. If any other unanticipated adverse events occur, the patient will be withdrawn from further participation in the study.

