1.4.2 Other Risks of Study Participation

There is the potential for loss of confidentiality for subjects participating in this study. However, every effort will be made to protect the confidentiality of subjects. After enrollment, patient identifiers will be linked to sequential numerical codes (Subject #1, #2, etc.). The detailed results of the research will be kept in a separate research file maintained by and accessible to only the investigators in a locked cabinet in [name] office. The numerical code key will also be maintained in a locked cabinet in [name] office and accessible only to investigators. If the patient is consented, and then withdraws from the study, their PHI will be discarded.

Furthermore, there is minimal risk of the electromyography (EMG) procedure. EMG is a noninvasive procedure which measures the compound muscle action potential (CMAP), experienced by the patient as a muscle twitch over the abductor pollicis brevis over the base of the thumb. EMG in this case will be measured by a surface electrode, which will be applied via an electrolyte gel and reinforced by tape. The patient may have a local allergic reaction to the gel and/or tape, which will be evaluated by the physician.

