3.1.1 Baseline clinical visit and seizure diary

We will enroll 14 patients who will undergo epilepsy surgery with expected subdural grid coverage over primary motor cortex. Potential subjects will be identified at the weekly multi-disciplinary epilepsy conference. Subjects must have a recent (<2 years) MRI scan, and registration of the TMS coil to the MRI scan via the Brainsight neuronavigation system will be utilized to guide TMS coil placement (Gugino et al 2001). When a presurgical fMRI is available which demonstrates the patient's hand knob, the fMRI will be used with the Brainsight neuronavigation system. Subjects will be recruited and consented during a presurgical clinical visit where the patient's primary epileptologist will introduce members of the research team.

Patients will be asked to keep a 7 day seizure diary prior to the TMS session.

3.1.2 nTMS mapping

Patients will receive a session of single-pulse TMS mapping of the motor area, at the outpatient TMS clinic at NYU Neurology Ambulatory Care Center, at [name] prior their epilepsy surgery, according to the following procedures:

- a. Determination of the motor threshold by (1) finding the most excitable region in the hand knob which elicits the strongest compound muscle action potential (CMAP) in the APB muscle; (2) finding the motor threshold by determining output stimulation intensity which generates peak to peak CMAP response above 50 mV in 5/10 stimulation cycles (Rossini et al., 1994).
- b. Concurrent EMG will be measured with electrodes placed at APB, abductor digiti minimi, flexor carpi radialis muscles. Reference electrode will be placed at the ipsilateral elbow above the brachial biceps muscle.
- c. Mapping of the upper extremity. After determination of the MT, mapping of the UE will be performed at 110% of the rMT. All positive and negative stimulation sites will be recorded and saved.

Patients will be closely monitored during TMS stimulation. Each subject will have a complete neurological examined by a neurologist before and immediately after nTMS. Patients will also be provided a side effects questionnaire after TMS mapping. Patients will then be asked to keep a 7 day seizure diary after the nTMS session

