8.1 Definitions

Unanticipated Problems Involving Risk to Subjects or Others

Any incident, experience, or outcome that meets all of the following criteria:

- Unexpected in nature, severity, or frequency (i.e. not described in study-related documents such as the IRB-approved protocol or consent form, the investigators brochure, etc)
- Related or possibly related to participation in the research (i.e. possibly related means there is a reasonable possibility that the incident experience, or outcome may have been caused by the procedures involved in the research)
- Suggests that the research places subjects or others at greater risk of harm (including physical, psychological, economic, or social harm).

Unanticipated Adverse Device Effect

An Unanticipated Device Effect is any serious adverse effect on health or safety, or any life-threatening problem or death caused by, or associated with a device, if that effect, problem, or death was not previously identified in nature, severity, or degree of incidence in the investigational plan or application (including a supplementary plan or application), or any other unanticipated serious problem associated with a device that relates to the rights, safety, or welfare of subjects.

Serious injury

Any injury or illness that is any one of the following:

- life-threatening
- results in permanent impairment of a body function or permanent damage to body structure
- necessitates medical or surgical intervention to preclude permanent impairment of a body function or permanent damage to a body structure

Adverse Event

(a) In parallel with recording the primary outcome, we will monitor for increase in seizure severity attributable to TMS by identifying all instances of generalized tonic clonic seizures after TMS treatments. Instances where seizure frequency increased after TMS will be reported to the IRB within 72 hours.

(b) If a self-limited, short (<5 min) partial seizure or evolution into generalized tonic clonic seizure occur, TMS mapping will stop for that day.

(c) If a secondarily generalized (convulsion starting in one area of body and then spreading to other areas) or 2 partial seizures occur during treatment, the patient will be withdrawn from further participation in the study.

(d) If any other unanticipated adverse events occur, the patient will be withdrawn from further participation in the study.

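### Rare adverse-event triggers withdraw a patient from the whole study rather than from nTMS, which on the ordinary reading ends the post-TMS seizure diary, and 8.1(b) and 8.1(c) disagree on a seizure that generalizes

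*Combined protocol and SAP*

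**What the plan says.** One mapping session is planned. Section 3.1.2 states: "Patients will receive a session of single-pulse TMS mapping of the motor area", and the phase table in 3.1 and visit 2 in 6.2 agree. A 7-day seizure diary is kept before the session and another after it. Section 3.3 makes these diaries the measure of safety and tolerability. After surgery, visit 3 (6.3) adds a neurological examination and a hand function questionnaire. Section 3.1.3 says this follow-up helps judge whether nTMS or DCS better predicts functional outcome.

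The adverse-event rules in 8.1 are:

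- (b) A short partial seizure, and likewise one that generalizes, leads only to a halt for the day: "evolution into generalized tonic clonic seizure occur, TMS mapping will stop for that day".
- (c) A secondarily generalized seizure, or a second partial seizure, while treatment is under way takes the patient out of the study.
- (d) The same consequence follows for anything else not foreseen: "If any other unanticipated adverse events occur, the patient will be withdrawn from further participation in the study".

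Section 1.4.1 repeats (b) as item 2 ("evolution into generalized tonic clonic seizures occur during the procedure, TMS mapping will stop for that day") and (d) as item 4. It has no item matching (c). The narrative before its list also withdraws patients for unanticipated events, but only those thought related to the intervention.

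The analysis population in 7.3 is patients who complete mapping and later undergo DCS. No separate safety population is defined.

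**The concern.** The withdrawal rule is written at the level of the study, not the device. After an in-session trigger no scheduled stimulation remains. What remains is observation: the post-TMS diary and the study part of the post-operative visit. Taken at its ordinary meaning, the rule gives up that observation and protects the patient from nothing that a stop to nTMS would not.

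Whether the diary is missing then depends on what happened to the patient under nTMS. A before-and-after diary summary based on the others can look better than the full group would. The diary also informs two safety actions. One is the IRB report in 8.1(a): "Instances where seizure frequency increased after TMS will be reported to the IRB within 72 hours". The other is the possible study pause for worsening seizure frequency in 8.4.

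The second issue is one of instruction. Two adjacent items treat a seizure that generalizes differently, so staff cannot tell whether that patient may be mapped on another day.

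**Working it through.** **1. The plan's own figure.** Section 7.1 takes 10 patients and adds about one third: 10 × 4/3 = 13.3, rounded up to 14. This reproduces and is not in dispute; 14 is the denominator below.

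**2. Who is withdrawn.**

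| Event | Disposition |
|---|---|
| One short partial seizure | Mapping stops that day (8.1(b), 1.4.1 item 2) |
| Seizure that generalizes | Stops that day (8.1(b), 1.4.1 item 2); also withdrawn (8.1(c)) |
| Two partial seizures during treatment | Withdrawn (8.1(c)) |
| Pain, transient hearing change | Medical follow-up (1.4.1 item 3) |
| Other unanticipated event | Withdrawn (8.1(d), 1.4.1 item 4; the 1.4.1 narrative requires suspected relatedness) |

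Because (b) stops mapping at the first partial seizure, the two-seizure trigger will rarely be reached in a single session.

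**3. What is lost and what is kept.** Kept: the examination and side-effect questionnaire at the session (3.1.2), the event itself, followed until it resolves or stabilizes (8.2), and reporting of serious and unexpected events to the IRB and the monitoring committee within 72 hours (10.1). The post-operative visit still takes place as routine care. Lost: the diary and the hand questionnaire. No section continues either after withdrawal.

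For generalized seizures, 1.4.1 item 1 watches for "generalized tonic clonic seizures after TMS treatments (defined as occurring within 20 minutes of stimulation"). That covers 20/(7 × 24 × 60) = 20/10,080 = 0.2% of the diary week. 8.1(a) states no time limit but schedules no data source, so the diary is the only scheduled seizure count for the rest of the week.

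**4. How many patients.** The documents give no rate for these triggers. For rate r, the expected number is 14r and the chance of at least one is 1 − (1 − r)^14.

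| r | Source | Expected | At least one |
|---|---|---|---|
| 1/980 | Paediatric single-pulse review cited in 1.2 | 0.014 | 1.4% |
| 1% | Assumed | 0.14 | 13% |
| 5% | Assumed | 0.7 | 51% |

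The first row counts seizures only and does not come from surgical epilepsy candidates.

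**5. What missing diaries do.** Each leaves 1/14 = 7.1 percentage points of the result unknown. Suppose no returned diary shows a rise (exact two-sided 95% limits):

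- One missing: the summary is 0/13, upper limit 24.7%. The full result lies between 0/14 (upper limit 23.2%) and 1/14 = 7.1% (interval 0.2% to 33.9%).
- Two missing: the summary is 0/12, upper limit 26.5%. The full result lies between 0% and 2/14 = 14.3% (interval for 2/14: 1.8% to 42.8%).

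These are bounds; nothing is assumed about what the missing diaries would have shown.

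**6. Effect on the nTMS-DCS comparison.** Falling below the 10 patients of 7.1 needs at least 5 withdrawals among 14. At 5% that binomial probability is 0.04%, and it is smaller at the lower rates.

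**The case against.** The best counter-argument is that the loss is inferred, rare and small. No section says observation stops at withdrawal, and 4.4.1, which lists when patients are taken out, names no adverse event. The only rate in the documents implies about a 98.6% chance that nobody is affected. Section 7.2 plans no diary test, and with 14 patients the limits are wide whatever happens. Releasing a patient, possibly a 12-year-old, from research duties after an unexpected event is a defensible, cautious choice. Rules (b) and (c) can also be applied in sequence: stop today, then withdraw.

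Much of this stands, and it keeps the severity low. It does not supply text that continues the diary. Caution is served as well by stopping nTMS, since patients and parents can still decline follow-up. Applying (b) and (c) together works only if one ignores that a stop limited to the day implies mapping may resume; 1.4.1 item 2 carries only that milder rule.

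Four stronger readings are tempting, and the documents do not support them:

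- *Everyone who reacts to nTMS is lost.* One short partial seizure, pain and hearing change do not trigger withdrawal. The other effects listed as known in 1.4.1, such as headache and syncope, are not unanticipated in kind.
- *The safety signal is hidden.* The triggering event is recorded, followed and reported, and under 10.1 a seizure alone may prompt a study pause. That decision does not wait for the diary.
- *A planned safety analysis or the primary comparison is biased.* No diary test is planned, and step 6 shows the comparison is hardly touched.
- *The withdrawn patient's data are destroyed.* Section 1.4.2 does say "If the patient is consented, and then withdraws from the study, their PHI will be discarded", but it speaks of a patient who withdraws, not of an investigator ending participation. Section 9.1 keeps information collected before authorization is revoked.

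One further point against stands: a patient whose session was cut short may fall outside 7.3 whatever 8.1 says. Rewording 8.1 alone would therefore not bring that diary into the reported safety data.

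**Conclusion.** The point holds in limited form. After the triggers in 8.1(c)-(d) and 1.4.1, study-level withdrawal adds no protection beyond stopping nTMS. It gives up the scheduled count of later seizures and the post-operative questionnaire in exactly the patients where they would be informative. The likely number is well below one patient: 0.014 to 0.7 expected across the rates tried, with 7.1 percentage points of diary uncertainty per patient lost.

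This rests on the ordinary meaning of withdrawal, on there being one session, and on illustrative rates, because the documents give none for these triggers. The conflict between 8.1(b) and 8.1(c) is in the text itself and needs no assumed rate. Overall this is a minor matter and a cheap improvement.

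**What to change.** 1. In 8.1(c), 8.1(d) and 1.4.1 (narrative and item 4), replace withdrawal from the study with: the patient receives no further nTMS. Continue the 7-day diary and the post-operative assessment with the hand questionnaire, unless the patient withdraws consent or, for a minor, a parent or guardian withdraws permission.
2. Add to 7.3 that safety is reported for everyone who received any nTMS pulse, giving diaries returned out of the number stimulated. Keep the existing completer set for the nTMS-DCS comparison.
3. Make 8.1(b) and 1.4.1 item 2 say that a seizure that generalizes ends all further nTMS, in agreement with 8.1(c).

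The cost is wording in the protocol, consent and assent forms, plus a few extra follow-up contacts with patients who had a triggering event. The diary and the visit are already planned, and the adverse effect record in 8.2 already asks whether study treatment was discontinued.

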8.2 Recording of Adverse Device Effects

At each contact with the subject, the investigator will record information on adverse device effects by specific questioning and, as appropriate, by examination. Information on all adverse device effects should be recorded immediately in the source document, and also in the appropriate adverse effect module of the case report form (CRF). All clearly related signs, symptoms, and abnormal diagnostic procedures results should be recorded in the source document, though should be grouped under one diagnosis.

All adverse device effects occurring during the study period will be recorded. The clinical course of each event should be followed until resolution, stabilization, or until it has been determined that the study treatment or participation is not the cause. Serious adverse device effects that are still ongoing at the end of the study period must be followed up to determine the final outcome. Any serious adverse device effects that occur after the study period will be recorded and reported promptly (see section 8.3 below) to the IRB, the device manufacturer (Magstim), and the FDA.

The minimum initial information to be captured in the subject's source document concerning the adverse device effect includes:

- Study identifier
- Study Center
- Subject number
- Device model and serial number
- A description of the event
- Date of onset
- Investigator assessment of the association between the event and study treatment
- Current status
- Whether study treatment was discontinued
- Whether the event is serious and reason for classification as serious

8.3 Reporting of Adverse Device Effects and Unanticipated Problems

8.3.1 Investigator reporting: Notifying the IRB

Federal regulations require timely reporting by investigators to their local IRB of unanticipated problems posing risks to subjects or others. The following describes the NYULMC IRB reporting requirements, though Investigators at participating sites are responsible for meeting the specific requirements of their IRB of record.

Report Promptly, but no later than 5 working days:

Researchers are required to submit reports of the following problems promptly but no later than 10 working days from the time the investigator becomes aware of the event:

- **Unanticipated problems including adverse events that are unexpected and related**
 - Unexpected: An event is “unexpected” when its specificity and severity are not accurately reflected in the protocol-related documents, such as the IRB-approved research protocol, any applicable investigator brochure, and the current IRB-approved informed consent document and other relevant sources of information, such as product labeling and package inserts.
 - Related to the research procedures: An event is related to the research procedures if in the opinion of the principal investigator, the event was more likely than not to be caused by the research procedures.
 - Harmful: either caused harm to subjects or others, or placed them at increased risk
- **Unanticipated adverse device effect**: Any serious adverse effect on health or safety or any life-threatening problem or death caused by, or associated with, a device, if that effect, problem, or death was not previously identified in nature, severity, or degree of incidence in the investigational plan or application (including a supplementary plan or application, or any other unanticipated serious problem associated with a device that relates to the rights, safety, or welfare of subjects.

Other Reportable events:

The following events also require prompt reporting to the IRB, though no later than 10 working days:

- **Complaint of a research subject** when the complaint indicates unexpected risks or the complaint cannot be resolved by the research team.
- **Protocol deviations or violations** (includes intentional and accidental/unintentional deviations from the IRB approved protocol) for any of the following situations:
 - *one or more participants were placed at increased risk of harm*
 - *the event has the potential to occur again*
 - *the deviation was necessary to protect a subject from immediate harm*
- **Breach of confidentiality**
- **Incarceration of a participant** when the research was not previously approved under Subpart C and the investigator believes it is in the best interest of the subject to remain on the study.
- **New Information indicating a change to the risks or potential benefits** of the research, in terms of severity or frequency. (e.g. analysis indicates lower-than-expected response rate or a more severe or frequent side effect; Other research finds arm of study has no therapeutic value; FDA labeling change or withdrawal from market)

Reporting Process

The reportable events noted above will be reported to the IRB using the Reportable New Information submission (including a description of the event with information regarding its fulfillment of the above criteria, follow-up/resolution and need for revision to consent form and/or other study documentation).

Copies of each report and documentation of IRB notification and receipt will be kept in the Clinical Investigator's study file.

8.4 Stopping Rules

Should a safety concern arise, the study will be voluntarily paused until further review. Specific events that may prompt a study pause are: exacerbation of seizure intensity or frequency, syncope, and/or exacerbation of underlying neurologic symptoms.

8.5 Medical Monitoring

It is the responsibility of the Principal Investigator to oversee the safety of the study at his/her site. This safety monitoring will include careful assessment and appropriate reporting of adverse events as noted above, as well as the construction and implementation of a site data and safety-monitoring plan (see section 9 Auditing, Monitoring and Inspecting). Medical monitoring will include a regular assessment of the number and type of adverse device events.

8.5.1 Data Monitoring Committee

The primary responsibility of data safety monitoring will lie with [name], although all members of her research team will have responsibility for DSMP. DSMP committee will meet in person or have telephone conversations every 2 months, and informally meet on an as needed basis. The DSMP will review patient safety, data quality, protocol compliance, and subject enrollment numbers. A summary DSMP report will be submitted to the IRB as part of the yearly continuation process. Reportable events will be reported in an expedited fashion, as described above in section 8.3.1. All team members have extensive experience in clinical neurophysiology as well as design and implementation of clinical trials, will participate:

NYU PI: [name]
 Assistant Professor of Neurology
 NYU School of Medicine
 Comprehensive Epilepsy Center

NYU Co- Principle Investigator: [name]

Assistant Professor of Neurology

NYU School of Medicine

Comprehensive Epilepsy Center

[name]

[name]

9. Data Handling and Record Keeping

All collected information will be secured in a locked office on a computer with password protection. No individual who is not part of this protocol will be given access to this information.

